# Management of children potentially at risk of TB (approximately 210 children) will be as follows (see also flow diagram, Appendix 12). Protocol amendment, January 2009.

- All children with a history of contact with a TB patient or with a positive T-spot.TB® result will be investigated for active TB: an X-ray will be performed and the child will be examined by a physician; any further investigations indicated (such as lymph node aspiration, gastric lavage) will be performed.
- Children with a history of TB disease which has been/ is being treated, or of isoniazid prophylaxis following exposure to a TB patient (expected number, <10): no additional treatment will be required.
- Children with untreated active tuberculosis (expected number, <5). These will be treated.
- Healthy household contacts of TB patients (expected number, ~111) who have never received isoniazid prophylaxis (whether T-spot.TB® positive or negative) will be treated with isoniazid prophylaxis for six months, in keeping with the National Tuberculosis Control Programme policy which recommends treatment of household contacts up to the age of five years.
- **Healthy HIV-positive T-spot.TB**®-**positive children** (expected number, <10). These will receive isoniazid prophylaxis.
- **T-spot.TB**®-**positive children with no history of exposure to TB patients** (expected number, ~74). This study will be among the first to identify healthy children with no history of exposure to a TB patient, but a positive T-spot.TB® response. The natural history of such a response (whether it is stable/ repeatable, and whether it will resolve spontaneously), the appropriate management, and the effect of isoniazid on such children, is unknown. Therefore children in this group will be randomised to receive isoniazid prophylaxis and monthly monitoring for 24 weeks or monthly monitoring only, and changes in the T-spot.TB® response will be investigated as indicated above. Children in the monitoring only group will be offered isoniazid prophylaxis from the age of six years if their T-spot.TB® response is still positive at that time.
- Adherence to isoniazid will be monitored by monthly pill counts and urine tests for isoniazid metabolites in all the treat children. Urine tests for isoniazid metabolites will also be performed in the T-spot.TB®-positive untreated group to detect any children who might be given isoniazid outside the study protocol.
- All children who are household contacts of a TB patient or T-spot.TB® positive will be seen monthly from age five to six years by a field worker for a simple health check and any that are sick will be referred to a physician for investigation and management.
- Children who are household contacts of a TB patient or T-spot.TB®-positive, will have liver function tests performed before isoniazid is commenced. If the results are abnormal, or

if isoniazid is contraindicated for any other reason (a history of convulsions or psychosis) they will not be treated but will be followed clinically for early detection of TB over the coming year.

To determine the effects of herpesvirus infections during early childhood on the ability of neonatal BCG immunisation to protect against TB infection.

Stored serum obtained annually from age one to five years will be examined using ELISA assays for IgG and IgM to Herpes simplex and cytomegalovirus in order to determine the age of first infection.

#### Interventions and exposures.

Aims 1 & 2. To examine the effects of maternal infection with intestinal nematodes or schistosomiasis, and of the treatment of maternal nematode infection or schistosomiasis in **pregnancy.** Mothers will be randomised to receive albendazole or placebo and praziguantel or placebo during the second to third trimester of pregnancy. A marked reduction in IFN-y response after BCG immunisation has been demonstrated for children of mothers with schistosomiasis or filariasis but the effects of intestinal nematodes, and the effects of treatment of helminths in pregnancy, including both intestinal nematodes and Schistosoma sp, are not known. We will determine the effect of intestinal nematodes by comparing children of mothers with and without intestinal nematodes during pregnancy (Appendix 4). If intestinal nematodes have an effect similar to schistosomiasis or filariasis, treatment of all or any of these groups of helminths in pregnancy may be beneficial for the response to immunisation in the neonate. This will be determined for individuals known to have had helminths before treatment, and for all participants (Appendix 4). If, however, treatment leads to an increase in type 2 bias, as has been documented in studies for schistosomiasis (Appendix 1, Figure 3), suppression of the neonatal type 1 response may be increased. For the same reason, treatment in pregnancy may have benefits, or disadvantages, for the neonate's susceptibility to bacterial or viral infections. For vertical transmission of HIV infection, treatment in pregnancy may have benefits for the immune response, or may enhance vertical transmission through a transient rise in viral load (Appendix 1, Figure 1). Thus, for our objectives, a randomised trial of treatment in pregnancy is appropriate. Other considerations are as follows. Treating hookworm in pregnancy can reduce anaemia,  so women with hookworm and severe anaemia will be excluded from randomisation and treated. Treating helminths may improve the mother's general health, and hence birth outcome (stillbirths, perinatal deaths, birthweight), but this has not been demonstrated in controlled trials; and there is a possible risk of teratogenicity, but this may be confined to the first trimester. Therefore, although these outcomes are not the main issue for this study, they will be recorded and considered in an interim analysis.

Aim 3. To examine the effects of acquisition of intestinal nematodes during childhood and of regular mass treatment in childhood. *After one year of age, children will be randomised to receive albendazole or placebo every 3 months. Both groups will receive annual, selective treatment based on stool analysis.* Prior helminth infection is associated with impaired responses to immunisation, but it is not certain whether acquisition of helminths leads to loss of an established response, or increased susceptibility to bacterial and viral infections, and whether this can be prevented by regular de-worming. This will be determined by comparing children who receive regular de-worming as well as annual, selective treatment with those who receive annual, selective treatment only (groups C1 vs C2, appendix 4). Prevention of helminth infections may have disadvantages, such as increased risk of severe malaria and thus, for our objectives, a randomised trial is appropriate. Other considerations are as follows. Regular de-worming may have benefits for growth and cognitive performance in childhood, but a recent meta-analysis has shown that the evidence, particularly relating to cognitive performance, is still inconclusive. Again, these outcomes are not the main issue for this study, but will be recorded.

**Aim 4.** To examine the effects of childhood schistosomiasis. This component will be observational because the incidence of schistosomiasis in children under 5 is not expected to be high enough to justify mass treatment. As in the case of intestinal nematodes, we wish to investigate whether acquisition of helminths leads to loss of an established response to immunisations, and influences susceptibility to other infections. For this observational component, important potential nutritional and environmental confounding factors for the effects of helminths are known to exist. These will be recorded and appropriate adjustments will be made.

Aim 5. To examine the effects of herpesvirus infections. Protocol amendment, January 2009. Since the start of our study, there has been new evidence that Herpesvirus infections early in life have a profound effect on the infant immune response. For example, in the Gambia, where 85% of children are infected with cytomegalovirus (CMV) by age one year, early CMV infection has been shown to alter maturation of the infant response, inducing a lymphocyte phenotype which suggests immune dysfunction in the elderly. We will therefore use stored serum from our cohort to investigate the age of infection with herpesviruses (Herpes simplex and CMV) in our community and to determine whether these infections influence the ability of BCG to protect against TB infection

#### Principal Outcomes.

**Outcome (1): immunological responses to childhood immunisations.** By studying responses to BCG, tetanus and measles, we will investigate a broad range of immunological responses. BCG evokes a polarised type 1 response, cytotoxic and antibody responses. Tetanus evokes an intermediate T-cell and antibody response which may demonstrate type 1 and type 2 switches more readily. For measles, CD8+ T-cell responses can be measured without restimulation *in vitro*.

We will use whole blood assays and antibody assays in all members of the cohort to evaluate the effect of helminths, and their treatment, on the development and maintenance of responses to BCG and tetanus immunisation. Whole blood assays can be used in large numbers of subjects and require small amounts of blood. They measure responses biased towards CD4+ T-cell, or nonspecific responses (monocyte, NK-cell, eosinophil or basophil). Mycobacterial antigens, tetanus toxoid and the mitogen phytohaemagglutinin (PHA) will be used for stimulation. The mycobacterial antigens will be whole cell lysate or culture filtrate proteins of *M. tuberculosis*, which are homologous between *M. tuberculosis* and *M. bovis* BCG, and early secreted antigen of *M. tuberculosis* (ESAT-6), which is specific for *M. tuberculosis*, to distinguish responses to immunisation and *M. tuberculosis* infection. We will measure the "type 1" cytokines, IFN- $\gamma$  and IL-2. Our results suggest that discrepancies between these two responses may be of particular interest: in HIV-1 positive adults, IL-2, but not IFN- $\gamma$ , responses were associated with increased risk of active tuberculosis; and IL-2 responses increased, while IFN- $\gamma$  responses declined, after treatment of schistosomiasis (Appendix 1, Figure 3). We will now determine whether helminth exposure has a differential effect on these two responses following immunisation. For "type 2" responses, IL-4 is seldom detectable in these assays in response to *M. tuberculosis* antigens, so we will measure IL-5 and IL-13 to examine whether helminths promote type 2 responses following immunisation. In mothers with schistosomiasis and their children, responses to vaccine antigens and to Schistosoma antigens will be compared, and we will also measure IL-10 and TGF- $\beta$  responses, to examine whether helminth-induced immunosuppressive cytokines have a role in helminth associated effects. Antibody responses can also be studied in large numbers of subjects. Our existing assays for mycobacterial antibodies and their subclasses will be extended to tetanus. If helminths promote type 2 responses to unrelated antigens we expect a predominance of IgG4 and IgE subclasses following immunisation.

We will use ELIspot assays to evaluate the effect of helminths, and their treatment, on CD8+ T-cell responses following BCG and measles immunisation. Approximately 30% of Ugandans possess

HLA-A2. Mothers and infants with HLA-A2 will be identified by flow cytometry using monoclonal antibodies, according to our current procedures (Appendix 5A), and confirmed by PCR-SSP with specific primers. Selected participants will then be studied, initially at 3-6 weeks after BCG or measles immunisation, since the precursor frequency for vaccine-specific T-cells may decline after this time point. ELIspot assays using selected HLA-A\*0201 binding peptides from BCG and measles will be used. We, and others, have detected responses to HLA-A\*0201 specific *M. tuberculosis* peptides by ELIspot for patients with tuberculosis (Appendix 5), If a response can also be detected following immunisation, ELIspot assays will allow enumeration of IFN- $\gamma$  and IL-4 producing CD8+ T-cells so that the effects of helminths on type 1/ type 2 responses by CD8+ T-cells can be examined. These assays will first be attempted in small numbers of subjects; the number required to obtain definitive results, and the best assays to use, will be determined by the preliminary results.

**Outcome (2): immunological responses to HIV in children of HIV-1 infected mothers.** Infants of HIV-infected mothers may be exposed to HIV in utero, at delivery or during breast-feeding. The neonatal immune response may have a role in determining vertical transmission. We will estimate the timing of HIV infection by DNA-PCR on blood spots from cord blood, and samples obtained at 6 weeks and 18 months after delivery. We will examine the effect of maternal helminth infections, and their treatment, on immune responses in cord blood and in infants at one year of age, by including HIV p24 antigen in the whole blood assay procedure. More detailed studies will be done on selected participants, using ELIspots or intracellular cytokine staining to identify responses by cell type and cytokine production. Cells will be stimulated with whole viral lysate, or with vaccinia constructs containing HIV genes to ensure class I presentation for CD8+ T cell responses. Potential confounding factors to be considered in these studies include possible associations between maternal helminth infection, or treatment of helminths, and maternal CD4+ T-cell count and viral load (Appendix 1), and the mother's choice of breast feeding practices. The numbers of subjects in the categories of maternal helminth infection and treatment will be small (Appendix 2 B), but will be sufficient to detect effects of a similar magnitude to those in our preliminary studies.

**Outcome (3): the incidence of infectious diseases in childhood.** The effect of maternal and childhood helminth infection on disease incidence and severity will be examined in the whole cohort, with helminth species analysed separately and together. Pneumonia (Acute lower respiratory tract infection, ALRI) will be defined by World Health Organisation criteria, based on cough, respiratory rate and chest indrawing. Malaria will be defined as fever with a parasite density above a cut-off set using standard methods. Diarrhoea ( $\geq$ 3 loose stools per day, or the mother's definition) will be recorded as the principal disease event when there is no evidence of another cause. Measles will be diagnosed clinically using standard criteria and confirmed by measurement of specific antibody. Children with suspected tuberculosis will be investigated in detail, using gastric aspirates or material from other sites, as clinically indicated. Microscopy will be performed using fluorescence microscopy, and cultures using BACTEC as well as Lowenstein Jensen medium, for greater sensitivity. Proposed algorithms and new diagnostic tests, including the Ligase Chain Reaction (LCR), and whole blood culture with ESAT-6 will also be used and evaluated. HIV infection will be diagnosed by serology and polymerase chain reaction (PCR) in children aged 1-2 years.

Protocol amendment, January 2009. *TB infection* will be added as an outcome. T-spot.TB® assays will be performed for all five and six year olds. These investigations will allow us to determine the prevalence of T-spot.TB®-positivity at age five and six years and, hence, to estimate the prevalence of *TB infection* at age five, and the incidence of TB infection between age five and six years.

The immunological response to schistosomiasis in children exposed to schistosomiasis in utero. Protocol amendment, January 2009. There is increasing evidence that exposure to helminth

infections in utero may modulate the development of immune response to helminths in the offspring and thereby influence susceptibility to both infection and disease induced by the same species. Such effects may be altered by treatment during pregnancy. We will therefore investigate in particular detail the effects of exposure to schistosomiasis, and to praziquantel treatment in utero, on the prevalence of schistosomiasis in children at age five years, and on the regulatory immune response in these children. Furthermore, these effects could "spill over" to influence the development of responses to other antigens such as allergens. This amendment has been developed to examine these possibilities by

1) Determining the prevalence and intensity of S. mansoni among the children at 5 years and effect of the treatment during pregnancy on these parameters.

Treatment of maternal schistosomiasis during pregnancy could affect the development of responses to schistosomiasis, and hence susceptibility to infection, in several ways. For example, increased *in-utero* sensitisation of the children might increase resistance to schistosomiasis infection and minimise disease morbidity. Reduced sensitisation or no sensitisation of the children might increase susceptibility of the children to infection and predispose to early and severe morbidity. Tolerance on the other hand, if it occurs, might be associated with increased susceptibility to infection as is the case in lymphatic filariasis. These possibilities will be examined by comparing the prevalence as well as intensity of *S. mansoni* infection between the children of women who were treated during pregnancy and those who were not, alongside children from uninfected women.

The collection of three stool samples at age five years in the nested cohort of *S. mansoni*-exposed children will allow us to fulfil this objective by improving on the sensitivity of parasitological stool analysis for the purpose of identifying any children infected with S. mansoni at 5 years.

2) Determining immune responses including regulatory T cell responses to schistosome antigens and allergen related antigens.

There may be important differences in the immune profiles between children of women treated during pregnancy and children of women who were not treated during pregnancy. These effects will be examined by determination of schistosome antigen-specific type 1 (IFN $\gamma$ ) and type 2 (IL-4, IL-5, IL-13) cytokine responses and antibody levels. Effects observed in the responses could be influenced by changes in regulatory immune responses. The regulatory immune responses will be examined by determination of schistosome antigen-specific Treg type 1 and Th3 cells as well as naturally occurring Tregs (nTreg) by intracellular cytokine staining (for IL-10, TGF $\beta$ , and FOXp3 respectively) and cell phenotype analysis (for CD3, CD4, and CD25 markers) by flow cytometry.

In-utero sensitisation to *S. mansoni* antigens may also influence immune responses to allergens since *S. mansoni* infection has been shown to be associated with low reactivity to mite allergens. Treatment of *S. mansoni* during pregnancy may have impact on responses to allergens among the children of the treated women. Indeed, recent data from [name] work within this study suggests that treatment of *S. mansoni* during pregnancy is associated with an increase in allergic disease events in infancy. This effect will be examined by determining plasma levels of immunoglobulin (Ig) G and IgE against antigen extracts of dust mites *Blomia tropicalis* and *Dermaphagoides pteronyssinus*.

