#### **Specific Aim:**

To examine the impact of helminths on the response to immunisation, and on susceptibility to infectious diseases in childhood, in a cohort of 2500 mothers and their children in Entebbe, Uganda. The study will have three randomised, placebo-controlled comparisons as well as observational components.

1. To examine the effects of maternal infection with intestinal nematodes, and of the treatment of maternal nematode infection in pregnancy. Mothers will be randomised to receive treatment with albendazole or placebo during the second to third trimester of pregnancy.

Mothers who are severely anaemic (haemoglobin  $\leq 8g/dl$ ) will be excluded from randomisation and treated with albendazole.

2. To examine the effects of maternal schistosomiasis, and of the treatment of schistosomiasis in pregnancy. Mothers will be independently randomised to receive treatment with praziquantel or placebo during the second to third trimester of pregnancy.

Mothers who have persistent diarrhoea with blood in the stools will be excluded from randomisation, investigated, and treated for schistosomiasis if present.

Thus the study will comprise four groups of mothers, according to treatment during pregnancy: (1) treated with both albendazole and praziquantel; (2) treated with only albendazole; (3) treated with only praziquantel; (4) no anti-helminthic treatment.

All mothers will have a second stool sample taken at delivery. All mothers will be mass treated with albendazole and praziquantel after delivery.

- **3.** To examine the effects of acquisition of intestinal nematodes during childhood and of regular mass treatment in childhood. After one year of age, children will be randomised to receive albendazole or placebo every 3 months. All children will receive annual, selective treatment based on stool analysis.
- **4.** To examine the effects of childhood schistosomiasis. This component will be observational. Children will receive annual, selective treatment based on stool analysis.

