#### Children: follow up visits.

A clinic at which mothers and children can be seen for follow up will be established in the renovated building at the Private Wing. Children will be seen there at scheduled follow up visits, or if they are sick.

Children will be seen routinely at their immunisation visits (6, 10 and 14 weeks) and then every three months up to the age of 18 months. This will allow their immunisations to be documented (at 6, 10 and 14 weeks, and then measles immunisation at 9 months) and their weight to be recorded. At first this will be done at the study clinic. Later it may be possible to devolve some of these visits to community clinics nearer to the mothers' homes. At one year mothers will be asked to give informed consent on behalf of the children for participation in the randomised, placebo controlled trial of three-monthly albendazole treatment. At 15 and 18 months they will receive their first two doses of albendazole or placebo. At 18 months blood samples will be obtained from children of HIV-positive mothers to ascertain the child's HIV status.

At routine annual follow up visits clinical data, blood for full blood count, malaria slide and immunological studies (2-5 ml) and stool samples will be obtained. Children found to have helminths in stool samples collected at annual visits will be treated by the field workers.

Protocol amendment, January 2009. At five years, 10 ml will be obtained to accommodate assessment of TB infection by T-spot.TB® assay and assessment of additional immune responses in children who were exposed to schistosomiasis in utero. At six years, 5 ml will be obtained for a T-spot.TB® assay.

Protocol amendment, January 2009. For more detailed assessment of schistosomiasis infection at the age of five years in children who were exposed to schistosomiasis in utero, three stool samples will be obtained from this subgroup of five year olds.

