#### *Follow up beyond five years of age.* Protocol amendment. March 2008.

It is possible that the interventions described above may have long term effects on children's growth and development, including their susceptibility to worm infections in later life, and their susceptibility to infectious, allergic and metabolic diseases. We will therefore continue observational follow up of our cohort in order to continue to document long-term outcomes. Nothing is known about the long term effects of these interventions, although it is clear that events in pregnancy and early life can have long term effects on health and development. Our initial results suggest possible opposing effects on susceptibility to infections and on susceptibility to allergic disease. These results need to be confirmed and expanded by longer follow up, into the age group where conditions such as asthma become important. The results are likely to have important implications for public health planning.

The additional follow up will be observational. The trial de-worming intervention in children (three-monthly albendazole versus placebo, with annual treatment in both arms for any children found to have worms) is completed at age five years. The aim is to determine the long-term effects of treatment provided during pregnancy and during the first five years of life. During the additional follow up to age 10 years children are expected to receive de-worming at school and in the community, according to national policy and procedures. This will be documented at annual visits, in retrospect, in accordance with current study procedure. Children will continue to have stool samples examined annually and to be treated if worms are found.

Children will continue to be seen at the study clinic for illness events between routine visits.

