- The delay in treating mothers randomised to treatment after delivery would be, at most, just over 7 months, since mothers would not be treated in the first trimester in any case. There appears to be no evidence that progression of disease caused by schistosomiasis is any faster in pregnant women than in other adults. Persistent diarrhoea with blood is considered to be the pathological effect of chronic schistosomiasis most likely to show an immediate response to treatment, so we have planned to exclude women with these symptoms from the study, investigate them, and treat them if schistosomiasis is found. Otherwise, chronic schistosomiasis, including hepatosplenic schistosomiasis, is frequently asymptomatic, or the symptoms are non-specific and often ignored. The severe sequelae of long-term, heavy infection, such as portal hypertension and oesophageal varices, are unlikely to be much affected by a delay in treatment of, at most, just over 6 months. Therefore, as far as we know, the delay in treatment in some mothers is unlikely to have serious adverse consequences for their health.
- The prevalence of schistosomiasis in the pilot study (>20%) would justify a mass treatment approach if treatment in pregnancy were found to be specifically beneficial to the mother or child. In addition, examination of the single stool sample obtained may detect only about 60% of infected mothers. Therefore we have proposed to study a mass treatment intervention in pregnancy rather than to use selective treatment.

Advice has been given by colleagues at the Ministry of Health, and Uganda Virus Research Institute (UVRI).

Protocol amendment, January 2009. The following additional ethical considerations relate to the introduction T-spot.TB® testing for TB infection among five and six year olds, and to the use of stored samples for investigation of herpesviruse infections.

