The results show a marked increase in the cytokine response to SWA following treatment, especially for IL-2 and IL-5, which was still present at 4 months. By contrast, the IFN- $\gamma$  response to CFP declined following treatment, while there was a transient increase in the IL-2 response and a small increase in the IL-5 response at 5 weeks, which coincided with the increase in viral load in these subjects.

Conclusions. Helminth infection showed a strong association with higher CD4+ T-cell counts and this appeared to reflect a more intact immune response to other antigens, rather than immune activation in response to the parasitic infection. The explanation for this association is not clear. Results following treatment are, however, in keeping with the hypothesis that persistent helminth infection may be associated with more rapid HIV progression, and that activation of parasite-specific immune responses may be associated with increased HIV replication and suppression of the IFN- $\gamma$  response to *M. tuberculosis*.

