#### APPENDIX 3: The impact of helminths on the response to immunisation and on susceptibility to infectious diseases in childhood in Uganda. Proposed Study Profile.

First visit to the antenatal clinic.

• Women who live in study area; no history of adverse effects of anti-helminthics.

Т

- Consent to study of treatment in pregnancy.
- Screening investigations, including Hb, HIV, RPR, immunological studies.
- Provision of antimalarials and haematinics.
- Request stool sample.

	↓
On receipt of stool sample; gestation > 14	weeks; screening Hb results available.

 
Severe anaemia:
 
Treat with albendazole; exclude
 
Persistent diarrhoea with blood:
 
investigate and treat; exclude
 
	
 
Not severe anaemia:
 
Randomise to albendazole or placebo & praziquantel or placebo
 

At delivery.	

 
Mother:
 
Blood and stool samples
 
Nevirapine if known HIV+
 
	

Child:

Cord blood

Nevirapine if mother known HIV+

Post delivery.	↓
• Mass treatment with albendazole and praziquantel; selective treatment for Strongyloides .	• 1-2 samples post immunisation for studies of time course of immune response in selected participants.
	 ▼
	At one year.
	
 
Blood and stool samples
 
Specific treatment for worms found
 
Consent to study of treatment in childhood.
 
Randomisation to receive albendazole or placebo at 3 month intervals, starting at age 15 months
 

	Annual visits.
	Blood and stool

- Blood and stool
- Specific treatment for worms found

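### Susceptibility to S. mansoni is judged only at age five, after infections found at earlier annual visits have been treated; this costs power and narrows what the result means

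*Protocol*

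**What the plan says.** The January 2009 amendment on schistosomiasis exposure in utero (Protocol, Principal Outcomes) asks whether treating the mother alters the child's susceptibility to S. mansoni. Objective 1 is "Determining the prevalence and intensity of S. mansoni among the children at 5 years and effect of the treatment during pregnancy on these parameters". The comparison is between "children of women who were treated during pregnancy and those who were not, alongside children from uninfected women". Three stools are taken at age five in the exposed children to improve detection.

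Elsewhere the protocol treats infections found before that age:

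- Specific Aim, item 3: all "children will receive annual, selective treatment based on stool analysis". Item 4 repeats this for childhood schistosomiasis.
- Children: follow up visits: "Children found to have helminths in stool samples collected at annual visits will be treated by the field workers".
- Appendix 3, from the one-year visit on: "Specific treatment for worms found".
- Follow up beyond five years of age describes the childhood trial as having run "with annual treatment in both arms for any children found to have worms".

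Objective 1 does not mention this treatment and does not use the stool results from ages one to four. Appendix 4 takes annual helminth results into account only for the childhood albendazole comparison.

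**The concern.** Susceptibility acts from birth, but the outcome is a snapshot at five. A child infected at two, found positive and cured counts the same at five as a child never infected. If one arm is more susceptible, more of its infections are found and cleared before the snapshot. Two things are at stake. Fewer infections remain to be counted, so the comparison has less power. And the result answers a narrower question (current infection under annual treatment) than the one asked. A null finding at five could be taken as no effect on susceptibility, although the annual stools that could show an earlier difference are already being collected.

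**Working it through.** The protocol gives no rate, sample size or power for S. mansoni at five, so there is no figure of its own to reproduce.

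**Inputs from the protocol**
- Infected mothers: 270 + 30 = 300 (Appendix 2B, 12% of 2500, stated as a minimum), so about 150 per praziquantel arm before losses.
- Single-stool detection about 60%: "examination of the single stool sample obtained may detect only about 60% of infected mothers" (Ethical Considerations). Using it for children is an assumption.
- Three stools at five. If independent, detection is 1 − 0.4³ = 93.6%.

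**Assumptions:** true risk ratio 2; yearly risk h as shown; full cure unless stated.

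**Step 1. Prevalence at five.** Let s = detection × cure at visits one to four. Prevalence before treatment at visit t is p(t) = (1−s)p(t−1) + h[1 − (1−s)p(t−1)]. With s = 0.6:
- h = 3%: 3.00, 4.16, 4.62, 4.79, 4.86%; × 0.936 = 4.5% detected.
- h = 6%: 6.00, 8.26, 9.10, 9.42, 9.54%; × 0.936 = 8.9% detected.
- With no childhood treatment: (1 − 0.97⁵) × 0.936 = 13.2% and (1 − 0.94⁵) × 0.936 = 24.9%.

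Annual treatment therefore cuts the difference at five from 11.7 to 4.4 percentage points. The ratio moves from 1.88 to 1.96, slightly nearer the true 2, because clearance limits saturation.

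**Step 2. Ever detected, ages one to five.** Never-detected children are those never infected, (1−h)⁵, plus those infected but missed every time. Infected and undetected before visit t: i(t) = 0.4 i(t−1) + h(1−h)^(t−1). For h = 3%, i(5) = 0.0447, so ever detected = 1 − 0.8587 − 0.0447 × 0.064 = 13.8%. For h = 6% it is 26.1%. The ratio is 1.89.

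**Step 3. Power** (two-sided 5%, 150 per arm) = Φ[(d − 1.96·SE0)/SE1], with SE0 the pooled and SE1 the unpooled standard error.
- At five: (0.0438 − 1.96 × 0.0290)/0.0288 = −0.45, so 33%.
- Ever detected: (0.1225 − 1.96 × 0.0462)/0.0456 = 0.70, so 76%.

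| Yearly risk | Detected at five | Ever detected | Power at five | Power, ever |
|---|---|---|---|---|
| 2% v 4%, constant | 3.1% v 6.0% | 9.4% v 18.1% | 23% | 59% |
| 3% v 6%, constant | 4.5% v 8.9% | 13.8% v 26.1% | 33% | 76% |
| 5% v 10%, constant | 7.5% v 14.5% | 22.2% v 40.2% | 50% | 92% |
| rising to 3% v 6% (weights 0.05, 0.25, 0.5, 0.75, 1) | 3.9% v 7.7% | 7.2% v 14.0% | 29% | 48% |
| rising steeply to 3% v 6% (weights 0, 0.1, 0.2, 0.5, 1) | 3.5% v 6.9% | 5.1% v 10.0% | 27% | 36% |

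At 3% v 6% constant, with cure at 80% or 60%, power at five is 38% or 44%, still against 76%. If the roughly 830 children of the TB component also bound this subgroup and 20% of mothers were infected (both assumptions), there are 83 per arm, and power is 20% against 51%.

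**Step 4. Share of age-five infection from the last year.** At low constant risk this is 1 ÷ Σ(1−s)^k, k = 0 to 4.
- Full cure, s = 0.6: 1/1.650 = 61%.
- 80% cure, s = 0.48: 1/2.004 = 50%.
- 60% cure, s = 0.36: 1/2.480 = 40%.
- Rising weights, full cure: 1/(1 + 0.3 + 0.08 + 0.016 + 0.001) = about 71%.
- Steep weights, full cure: 1/(1 + 0.2 + 0.032 + 0.006) = 81%.
- No treatment: 20%.

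Intensity was not modelled.

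**The case against.** A reader might infer that annual treatment biases the comparison towards equality. It does not on the relative scale: Step 1 shows the ratio kept close to 2. Treatment follows the same rule in both arms, so the randomised test is valid when there is no effect. The loss is in absolute difference and power.

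A reader might also infer that age five reflects only the last year. Imperfect detection and cure carry earlier infections forward, and at 60% cure the last-year share is about 40%.

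The power gap depends on the age pattern. The Background calls helminth infection rare in infants. If exposure starts late, age five is a sensible time to measure, and the cumulative outcome gains only from 27% to 36%. That stands, although the cumulative outcome had more power in every scenario run.

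For objective 2, one might argue that earlier treatment distorts immune responses at five, since Appendix 1 reports that "The results show a marked increase in the cytokine response to SWA following treatment". Those data come from HIV-positive adults followed to four months; the last scheduled treatment here falls about a year before the age-five blood sample. Treatment prompted by infection is also a consequence of the randomised arm, hence part of its total effect. The documents do not show a bias in objective 2.

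Finally, the amendment does state age-five prevalence as its aim, nothing bars other use of the annual stools, and an analysis plan might add it. But the protocol itself ties susceptibility to this one time point.

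**Conclusion.** The point holds as a loss of power and a limit on interpretation. Age-five infection is current infection under annual selective treatment. Roughly 40 to 70% of it would be from the last year under constant or moderately rising risk, and more if risk rises steeply. The comparison is valid and its ratio sound, but at a true ratio of 2 and 150 per arm, power at five runs from 23% to 50% in the tabulated scenarios, against 36% to 92% for ever positive. Childhood incidence, cure, detection in children and the number reaching five are all assumptions, so the direction is firmer than any single figure. The case supports adding a cumulative outcome. It does not support displacing the age-five one, which has three stools and egg intensity behind it.

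**What to change.** Keep prevalence and intensity at five, and describe them as current infection under annual selective treatment. Add to objective 1 a pre-specified comparison of ever positive for S. mansoni (or time to first positive annual stool) from age one to five, between the randomised praziquantel arms within mothers found infected in pregnancy. State that a null result at five alone will not be read as no effect on susceptibility. As context for objective 2, report by arm how many children were treated for S. mansoni before five.

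The cost is amendment wording and a little analysis; sampling and care do not change. There are two downsides. Stools at ages one to four are single, less sensitive samples, though equally so in both arms. And many had been collected by January 2009, while Appendix 9 already planned unblinded analyses that include parasitology in babies at one year. The new comparison should therefore be labelled as added by amendment and specified before the annual S. mansoni results are examined by arm, and the amendment should say if any already have been.
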